Rationale:	
There is a wealth of evidence to support the benefits of oxygen therapy on wound healing¹⁻⁷. Oxygen is required for all major processes of wound healing and wound hypoxia is common. Skin wounds can receive oxygen from the blood stream via perfusion and from oxygen uptake through the skin. Yet, both wound perfusion and blood oxygen levels are frequently insufficient in patients with chronic wounds due to poor circulation, vascular disruption, and vasoconstriction, thereby reducing the wound's capacity to heal.
 
Diabetic ulcers, vascular ulcers (venous or arterial), and pressure injuries are all chronic wounds. The pathologies underlying chronic wounds can differ widely. However, common shared features include prolonged or excessive inflammation, persistent infections, and the inability to respond to reparative stimuli^{8,9}. Adults with vascular disease and/or diabetes are at highest risk for chronic leg and foot wounds. The ischemic (reduced tissue perfusion) and/ or hypoxic lower limb conditions which result from these conditions reduces availability of both oxygen and nutrients, making these wounds especially hard to heal. These wounds last on average 12 to 13 months, but this varies widely; many will remain open for years or never heal^{8,9}, and up to 30% of DFUs go onto amputation¹⁰. Even when they do heal, wounds recur in 60-70% of patients, decrease quality of life, and are a significant cause of morbidity^{8,9}.
 
The need for telehealth and remote patient monitoring in the current climate is critical and reinforces the VA's strategy to protect and care for Veterans, their families, health care providers and staff in the face of this pandemic. The VA's tactic to shift outpatient care to a "telehealth" mode, with phone, video and/or electronic communication to meet the needs of the ambulatory patient is difficult to achieve in wound care as clinicians relies heavily on the visual appearance of the wound to direct their therapy decisions. Thus, it is imperative to validate a remote monitoring tool that offers standard telehealth care as well as accurate, consistent, and simple wound measurement and imagery. Having the ability to manage complex wounds accurately should enable quick identification of early warning signs that the wound is deteriorating thus facilitating appropriate triaging of patients that need urgent face to face medical review.

Study Design:	Consecutive case series

Patient population	6 - 12 patients meeting eligibility criteria
Number of Sites:	Single Site
Inclusion criteria: Patients must fulfil all the following criteria to be eligible for inclusion into the study:	
 1. Male or female 18 years of age and older 2. Subjects having a non-healing wound of any etiology, except 3rd degree burns 3. No visible signs of healing objectively, less than 30% reduction in wound size in the last 4 weeks 4. Wound present for at least 4 weeks but less than 12 months 5. Subjects' wound size is minimum of 1 cm² and maximum of 25cm² 6. Subject is able and willing to participate in self care 7. Subject is able and willing to follow the protocol requirements 8. Subject has signed informed consent
Exclusion criteria Patients who met any one of the following criteria during screening visit are not eligible to participate into the study:	
 1. Subject has a life expectancy < 1 year 2. Subject is unable to manage the NATROX® device (charge and change the batteries daily) 3. Subject unable or reluctant to use iPhone and imaging technology 4. Subject has ulcers that are completely necrotic or if the clinician felt it was clinically necessary to cover the wound surface in gel or creams that would prevent the transmission of oxygen to the wounds surface 5. Subject has major uncontrolled medical disorder(s) such as serious cardiovascular, renal, liver or pulmonary disease, lupus, palliative care or sickle cell anemia; 6. Subject currently being treated for an active malignant disease or patients with history of malignancy within the wound 7. The subject has other concurrent conditions that in the opinion of the investigator may compromise subject safety 8. Known contraindications to the NATROX® 9. Known allergies to any of the NATROX® components 10. Known allergies to adhesives
Discontinuation criteria	
 1. Signs of allergic or hypersensitivity to any components of NATROX® 2. Onset of any condition that could severely interfere with investigational treatment evaluation 3. Investigator's decision to withdraw the patient 4. Patient's decision to withdraw consent 5. Need to use a prohibited medication/therapy
Endpoints	
Primary endpoint:
 
 - Number of participants that achieve complete wound closure during the 12-week study

	
 - The percentage change in ulcer size at 12 weeks relative to baseline measurement – this parameter will be performed using the eKare platform. 
Secondary endpoint: The effectiveness of the remote management tool for:
 
 - Reducing number of face to face clinic visits necessary - Improved communication between hospital and home around wound progression - Ease of implementation and acceptance by the patient - Early warning and triaging wound issues - Increase confidence in proactively managing patient remotely
Method:	
Prior to recruitment participants should have clinical documentation of wound progression for a minimum of 2 weeks, including wound measurements, if accurate data unavailable, participants wound progression will be monitored for 2 weeks prior to therapy intervention. Wound debridement and the use of off-loading, where appropriate will be at the discretion of the wound specialist throughout the study. On recruitment a full wound assessment will be completed in the eKare platform, this will act as the point of reference. Participants will be commenced on NATROX® Oxygen Wound Therapy with an adhesive foam dressing as a secondary dressing, frequency of dressing changes will be dictated by exudate levels and clinical judgement. The participant will be given a specially configured iphone (eKare patient App and NATROX® Patient library) along with any relevant personalised instructions, this could include a video of their dressing regime to support self application.
 
For the first 4 weeks following recruitment, wounds will be monitored remotely by the wound specialist with a face to face clinical reviews every 2 weeks. Patients will be instructed to photograph the wound via the eKare app at each dressing change (minimum of once weekly) which will be transmitted to the wound specialist. Following the initial 4 weeks of therapy, face to face clinical reviews can be extended to every 4 weeks, based on clinical judgement.
 
Participant will have a weekly clinical review performed via the eKare app for the duration of the study or till the wound heals, whatever comes first. Prior to the weekly review, patient will be asked 5 questions (with yes or no answers only) to help identify early warning signs of wound problems along with any compliance issues with the chosen therapy. During the study if self application, compliance, or wound issues are identified by either the participant or highlighted through the eKare monitoring tools, participants can be triaged for additional clinical intervention or support as deemed appropriate.

References

2. Babior, B.M. (1978) Oxygen-dependent microbial killing by phagocytes (first of two parts). *New England Journal of Medicine*. 298, 659-668.

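### Closure counts as a primary-endpoint success without confirmation, and the judgement that a wound has healed ends the weekly review that could contradict it

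*Protocol*

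**What the plan says.** The Endpoints row of the Protocol gives as its first primary endpoint the "Number of participants that achieve complete wound closure during the 12-week study". It does not say what complete closure is, who judges it, by what means, or whether it must be seen more than once. The second primary endpoint, percentage change in ulcer size, is fixed at week 12 and names the eKare platform as its instrument.

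The Method row describes two streams of observation:

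- **Remote.** Patients photograph the wound through the app at dressing changes, at least once a week, and the images go to the wound specialist. There is a "weekly clinical review performed via the eKare app for the duration of the study or till the wound heals, whatever comes first".
- **Face to face.** Reviews are every 2 weeks for the first 4 weeks. After that, "face to face clinical reviews can be extended to every 4 weeks, based on clinical judgement".

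The design is a "Consecutive case series" of "6 - 12 patients meeting eligibility criteria". The Rationale says of chronic wounds: "Even when they do heal, wounds recur in 60-70% of patients".

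**The concern.** Two provisions that are harmless alone work badly together. The endpoint can be met at any moment in the 12 weeks, and the routine weekly observation ends when it appears to have been met. If the first evidence is a home photograph, the same reading may both score the participant as a success and close the stream of images most likely to show that the reading was wrong or that the wound had reopened.

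The error runs in one direction. A false or brief closure adds a success, and nothing in the endpoint takes one away. There is no comparison group in which the same error would occur and partly cancel. The closure count is a headline result of a very small series, so one participant moves it visibly.

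A statistical analysis plan could define how closure is scored, but it could not recover weekly looks that the protocol has stopped collecting.

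**Working it through.** The Protocol gives no sample-size, precision or error-rate figure for closure, so there is no stated number to reproduce. The check has three parts.

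**1. When a closure can be seen, and what follows it.** Inputs are the review intervals in the Method row. At the widest spacing allowed, face-to-face reviews fall at weeks 2, 4, 4 + 4 = 8 and 8 + 4 = 12. A closure first read from a photograph soon after the week-8 review can wait nearly 4 weeks for the next in-person look, and one first read at week 9 waits 12 − 9 = 3 weeks. In that gap the weekly remote review is no longer required, because the wound has been judged healed. The wider spacing is optional, so the gap may be shorter.

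**2. The size of one error.** The denominator is 6 to 12 (Patient population row). One extra success adds 1/n:

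- n = 12: 1/12 = 8.3 percentage points. For example, 5/12 = 41.7% becomes 6/12 = 50.0%.
- n = 6: 1/6 = 16.7 percentage points. For example, 2/6 = 33.3% becomes 3/6 = 50.0%.

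**3. How a first-reading rule accumulates errors (illustration only).** Let f be the chance that one review of an open wound is read as closed. This rate is not in the Protocol; it is assumed here, from 0.5% to 5%. Assume k = 12 independent weekly reviews, wounds that stay open, and no correction at a clinic visit. If the first closed reading counts, the risk per patient is 1 − (1 − f)^k. The chance of at least one false closure among n such patients is 1 − (1 − risk)^n. For comparison, the last column requires two consecutive closed readings.

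| Assumed f | Risk per patient, first reading | At least one, n = 6 | At least one, n = 12 | Risk per patient, two consecutive readings |
|---|---|---|---|---|
| 0.5% | 5.8% | 30.3% | 51.4% | 0.03% |
| 1% | 11.4% | 51.5% | 76.5% | 0.11% |
| 2% | 21.5% | 76.7% | 94.5% | 0.43% |
| 5% | 46.0% | 97.5% | 99.9% | 2.6% |

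With f = 1% and only 6 reviews, the first-reading risk per patient is 1 − 0.99^6 = 5.9%, and the chance of at least one is 30.4% (n = 6) or 51.5% (n = 12).

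The table shows the mechanism and does not estimate the bias in this trial. It overstates the problem where wounds truly close or clinic visits correct a reading. It overstates the benefit of a second photograph if the same wound is misread the same way twice, which is why one of the two looks should be in person.

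**The case against.** The strongest reply is that the Protocol is silent here rather than wrong. It nowhere says that one observation is enough, operational scoring is often left to an analysis plan, and the listed Schedule of Events is not shown and might hold a closure visit. This stands in part: a single-look rule is an inference from the at-any-time wording and the absence of any confirmation step. It does not dispose of the point, because the rule that ends weekly review at healing is written in the Method row itself.

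Several stronger readings are tempting, and the documents do not support them:

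- **That a misread closure is never challenged.** Healing ends only the weekly app review. Nothing says that face-to-face reviews or the week-12 size measurement stop, and either could expose an error. What is true is that neither is tied to confirming closure and neither would reverse the count.
- **That no closure in the last two weeks can be confirmed.** One first seen in week 11 could be checked at week 12. Only one first seen at the final assessment has no later look.
- **That the 60–70% recurrence figure shows transient closure to be common in this study.** It has no time frame and concerns wounds that did heal. It says nothing about misreading, or about reopening within 12 weeks.
- **That the tool still to be validated is the instrument for closure.** eKare is named only for percentage change in size. A wound specialist reads the images, although that reading may rest on a home photograph alone.

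It is also fair to say that 1/n is the effect of any single misclassification, and that extra visits or follow-up past week 12 would alter the study and cut against its secondary endpoint of fewer clinic visits. Both remarks stand and limit the remedy.

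**Conclusion.** The point holds in a limited form. Closure at any time in the 12 weeks counts, no confirmation is required, and the judgement of healing ends the only assured weekly observation that could contradict it. Each false or transient closure adds 8.3 to 16.7 percentage points to the closure proportion, always upward. How many there would be is unknown: the Protocol offers no misreading rate and no 12-week reopening rate.

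The conclusion rests on two readings: that the endpoint wording means at any time, and that review ending at healing means just that. A confirmation visit in the unseen Schedule of Events would weaken it. Since the remedy can use observations already scheduled, the change is worth making despite the uncertain size.

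**What to change.** - In the Method row, continue the weekly eKare photograph and review to week 12 for every participant, including after first apparent closure. Word the photograph instruction so that it does not lapse when dressing changes stop.
- In the Endpoints row, count a closure as confirmed only if the wound is still closed at a later look, with at least one of the looks being an already scheduled face-to-face review. State that the week-12 assessment can serve as that review.
- Date the closure at the first look.
- Report closures first seen too late to confirm by week 12 separately as unconfirmed. Do not extend the study or add visits for them.

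The cost is an amendment to two rows, a few more photographs and remote reviews per healed participant, and a confirmed-closure count that may be slightly lower than the unconfirmed one.
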